5.4.3 Supportive Care Guidelines

Supportive care, including infection prophylaxis will be conducted as per the current University of Utah institutional BMT program clinical practice guidelines.

Steroids can be re-introduced for supportive care once the taper begins as long as it is cleared with the Principle Investigator, is not for the treatment of GVHD progression AND does not exceed 0.5 mg/kg/d PDE.

5.5 Duration of Therapy

In the absence of treatment delays due to adverse event(s), treatment may continue for up to 12 cycles (i.e. 12 months) if there is clinical benefit (i.e. PR or CR) after the first 6 cycles, (i.e. 6 months) or until one of the following criteria applies:

- Chronic GVHD or malignancy progression,
- Intercurrent illness that prevents further administration of treatment,
- Unacceptable adverse event(s) (see section 6.1)
- Patient decides to withdraw from the study, or
- General or specific changes in the patient's condition render the patient unacceptable for further treatment in the judgment of the investigator.

5.6 Duration of Follow Up

Patients will be followed for a total of 6 months after removal from study treatment or until death, whichever occurs first. Patients removed from study for unacceptable adverse event(s) will be followed until resolution or stabilization of the adverse event.

5.7 Criteria for Removal from Study

Patients will be removed from study when any of the criteria listed in [Section 5.5](#) applies. The reason for study removal and the date the patient was removed must be documented in the Case Report Form. In addition, early stopping criteria are defined in Section 9.

6 DOSING DELAYS, DOSE MODIFICATIONS AND EARLY STOPPING CRITERIA

This study will utilize the CTCAE (NCI Common Terminology Criteria for Adverse Events) Version 4.0 for adverse event and serious adverse event reporting. A copy of the CTCAE Version 4.0 can be downloaded: (<http://safetyprofiler-ctep.nci.nih.gov/CTC/CTC.aspx>).

6.1 Dose Modifications

In the case of any Grade 2 hematologic or non-hematologic toxicity attributable to the study drug, dose reductions can be performed to up to 3 different, consecutive levels as detailed below. All initial dose reductions will start at level -1, and proceed to the immediately lower level if the toxicity in question persists for at least 1 week. Dosing

schedules will be dependent on what day of the week the patient starts the dose reduction level; for example, patients on Dose Level -1 with a Monday start would dose on Wednesday, Friday, Sunday, and so on.

Dose reduction levels are:

- Level -1 (150 mg every other day)
 - Level -2 (150 mg every three days)
 - Level -3 (150 mg twice a week)
-
- GDC-0449 will be discontinued under the following circumstance:
 - Grade 3 or 4 non-hematologic or hematologic toxicity attributable to study treatment by Common Terminology Criteria for Adverse Events (CTCAE) version 4.

8 STUDY PROCEDURES

Patient registration for this trial will be managed by the Research Compliance Office at the Huntsman Cancer Institute.

Assessments performed exclusively to determine eligibility for this study will be done only after obtaining informed consent. Assessments performed for clinical indications (not exclusively to determine study eligibility) may be used for baseline values even if the studies were done before informed consent was obtained.

8.1 Screening Procedures

All screening procedures must be performed within 7 days prior to registration unless otherwise stated. The screening procedures include:

- Informed Consent
- Medical history - Complete medical and surgical history, including history of infections
- Demographics - Age, gender, race, ethnicity
- Review subject eligibility criteria
- Review previous and concomitant medications
- Physical exam including vital signs, height and weight - Vital signs (temperature, pulse, respirations, blood pressure)
- Performance status - Evaluated prior to study entry according to [Appendix A](#).
- Adverse event assessment - Baseline adverse events will be assessed. See [Section 14.0](#) for Adverse Event monitoring and reporting.
- Hematology
 - Complete blood count (CBC) with differential and platelet count.
- Blood draw for correlative studies
 - See [Section 13.0](#) for details.
- Blood Serum chemistries
 - Comprehensive metabolic panel (CMP) to include: albumin, alkaline phosphates, Alanine Amino transferase/Serum Glutamic Pyruvic Transaminase(ALT/SGPT), Aspartate Amino transferase/ Serum Glutamic Oxaloacetic Transaminase(AST/SGOT), BUN, creatinine, electrolytes (sodium, potassium, calcium, chloride, bicarbonate), glucose, and total bilirubin.
 - Serum Magnesium (Mg) and Phosphorus (Phos).
 - Serum Lactate dehydrogenase (LDH).
 - Pregnancy test (for females of child bearing potential)
- Chronic GVHD assessment
- To be performed using the NIH global score which will be defined by using the NIH consensus criteria for assessment of chronic GVHD severity [46].

Other tests

- Baseline pulmonary function tests.

8.2 Procedures During Treatment

Clinical assessment visits - Will be scheduled monthly for the first 3 months, then months 4, 6, 8, 10, 12 while patients are receiving GDC-0449 and will include history and physical exam (H&P) including vital signs, height and weight, directed evaluation of chronic GVHD assessment as per [8.1](#), directed evaluation of treatment effect as per [9.0](#), directed evaluation of adverse events as per [14.0](#), hematology as per [8.1](#), serum chemistries as per Section [8.1](#).

Study endpoint assessments - Will be study specific and will include comprehensive evaluations of chronic GVHD and evaluations of correlative studies as in table in [section 7](#).

8.3 Follow-Up Procedures

Patients will be followed every 3 months from the first day the patient is no longer receiving GDC-0449 through 6 months from the completion of GDC-0449.

Follow-up visits will include H&P including vital signs, height and weight, directed evaluation of chronic GVHD assessment, directed evaluation of treatment effect, directed evaluation of adverse events, hematology and serum chemistries following the same guidelines above in [section 8.1](#).

8.4 Time and Events Table

The time of assessments is shown in months, as it facilitates better comprehension, preventing potential errors, in the interpretation of the exact timing for each assessment. On the other hand, in order to facilitate integration with the weekly-based schedule of corticosteroids taper, and also budget considerations, we use the following transformation between weeks and months when addressing the schedule of assessments:

1 month:	Week 4+/-1 week
2 months:	Week 8+/-1 Week
3 months:	Week 12+/-1 week
4 months:	Week 16+/-1 week
6 months:	Week 24 +/-1week
8 months:	Week 32+/- 1 week
9 months:	Week 36 +/-1 week
10 months:	Week 40 +/- 1 week
12 months or 1 year:	Week 52 +/-1week
15 months:	Week 64 +/-1 week
18 months:	Week 72+/-1 week

9 CRITERIA FOR EVALUATION AND ENDPOINT

9.1 Measurement of Effect

Response to therapy will be assessed at clinical assessment visits every 3 months from the first day of treatment with GDC-0449 through 12 months from the initiation of GDC-0449. Response will be defined as FFS at 6 months [23].

9.1.1 Failure Free Survival Definition

FFS is defined as being alive and:

- No relapse of malignancy
- No addition of any other systemic treatment for chronic GVHD
- Steroid dose at 6 months \leq 0.2 mg/kg/day PDE

The need for addition of therapy while on GDC-0449 is one of the criteria for failure, and consequently the patient will be taken off study. In order to minimize differences in practice that might impact the primary endpoint, we established minimal indispensable criteria to initiate additional immunosuppressive therapy during the first six months of GDC-0449 treatment.

9.1.2 Definition of Response to Therapy

1. Stable disease (SD) (no change in chronic GVHD) according to NIH consensus response criteria for a total of 1month [46]. This criteria is irrespective of any response obtained initially, prior to the month of stability.
2. Progressive Disease: This is defined as any one of the following:
 - Skin: Increase in NIH Skin Score by 1 or more points, except 0 to 1.
 - Eyes: Increase in NIH Eye Score by 1 or more points, except 0 to 1.
 - Mouth: Increase in NIH Modified Oral Mucosa Rating Score of 2 or more points.
 - Esophagus: Increase in NIH Esophagus Score by 1 or more points, except 0 to 1.
 - Upper GI: Increase in NIH Upper GI Score by 1 or more points, except 0 to 1.
 - Lower GI: Increase in NIH Lower GI Score by 1 or more points, except from 0 to 1.
 - Liver: Increase by 2x ULN ALT, alkaline phosphatase, and Total bilirubin.
 - Lungs: Decrease by 10% predicted absolute value of %FEV1. If PFTs not available, increase in NIH Lung Symptom Score by 1 or more points, except 0 to 1.
 - Joints and Fascia: Increase in NIH Joint and Fascia Score by 1 or more points or decrease in P-ROM score by 1 point for any site.
 - Global: Clinician overall severity score increases by 2 or more points on a 0 – 10 scale
3. Partial Response: This is defined as any one of the following:
 - Skin: Decrease in NIH Skin Score by 1 or more points
 - Eyes: Decrease in NIH Eye Score by 1 or more points
 - Mouth: Decrease in NIH Modified Oral Mucosa Rating Score of 2 or more points.
 - Esophagus: Decrease in NIH Esophagus Score by 1 or more points.
 - Upper GI: Decrease in NIH Upper GI Score by 1 or more points
 - Lower GI: Decrease in NIH Lower GI Score by 1 or more points.
 - Liver: Decrease by 50% ALT, alkaline phosphatase, and Total bilirubin.
 - Lungs: Increase by 10% predicted absolute value of %FEV1. If PFTs not available, decrease in NIH Lung Symptom Score by 1 or more points.
 - Joints and Fascia: Decrease in NIH Joint and Fascia Score by 1 or more points or increase in P-ROM score by 1 point for any site.

- Global: Clinician overall severity score decreases by 2 or more points on a 0 – 10 scale.
4. Complete Response: This is defined as any one of the following:
- Skin: NIH Skin Score 0 after previous involvement.
 - Eyes: NIH Eye Score 0 after previous involvement.
 - Mouth: NIH Modified Oral Mucosa Rating Score 0 after previous involvement.
 - Esophagus: NIH Esophagus Score 0 after previous involvement.
 - Upper GI: NIH Upper GI Score 0 after previous involvement.
 - Lower GI: NIH Lower GI Score 0 after previous involvement.
 - Liver: Normal ALT, alkaline phosphatase, and Total bilirubin after previous elevation of one or more.
 - Lungs: Normal %FEV1 after previous involvement. If PFTs not available, NIH Lung Symptom Score 0 after previous involvement.
 - Joints and Fascia: Both NIH Joint and Fascia Score 0 and P-ROM score 25 after previous involvement by at least one measure.
 - Global: Clinician overall severity score 0.

Patients under categories 1 and 2 require the addition of other systemic treatment for chronic GVHD. These conditions should be attributable to chronic GVHD, with exclusion of other relevant causes in the differential diagnosis when applicable. The addition of other systemic treatment excludes the patient from the current clinical study.

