5.3 Other Immunosuppression

5.3.1 Corticosteroids

Corticosteroids at a dose of >0.5 mg/kg/d PDE for at least 1 week prior to initiation of GDC-0449. After initiation of GDC-0449, the corticosteroids will be tapered according to protocol guidelines in the following table, in order to minimize heterogeneity and subsequent potential for confounding:

Week	PDE (mg/kg)
0 Start of therapy	1 daily until at least 1 week after clinical improvement
1 to 2 (starting at least 1 week after clinical improvement)	1 alternating with 0.5
3 to 4	1 alternating with 0.25
5 to 6	1 every other day (maintain until resolution of GVHD)
7 to 8 (start after resolution or near resolution of GVHD)	0.7 every other day
9 to 10	0.5 every other day
11 to 12	0.4 every other day
13 to 14	0.3 every other day
15 to 16	0.2 every other day
17 to 18	0.1 every other day

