10.1.1 Primary Endpoint

- FFS at 6 months after initiation of therapy with GDC-0449
FFS is defined as absence of NRM, no recurrent malignancy, steroid dose at 6 months ≤ 0.2 mg/kg/d of PDE, and no addition of new systemic treatment for chronic GVHD (Adapted from [45]). Criteria for addition of new systemic treatment for chronic GVHD are defined as per [section 9.0](#).

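### As worded, 9.1.2 can class a resolved or near-resolved patient who holds that state for a month as stable disease, and so as a 6-month FFS failure

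*Combined protocol and SAP*

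**What the plan says.** - **SD.** Section 9.1.2, category 1, is one month with no change in chronic GVHD. No reference assessment (baseline or best score) is named. The definition adds: "This criteria is irrespective of any response obtained initially, prior to the month of stability".
- **Consequence.** The closing paragraph of 9.1.2 states: "Patients under categories 1 and 2 require the addition of other systemic treatment for chronic GVHD". Categories 1 and 2 are SD and progressive disease (PD). Adding such treatment takes the patient off the study. The same paragraph says the condition should be attributable to chronic GVHD once other causes are excluded.
- **Link to the endpoint.** Section 9.1.1: "The need for addition of therapy while on GDC-0449 is one of the criteria for failure". It presents the criteria as governing the first six months on drug, and as a way to limit practice differences that could affect the primary endpoint. Section 10.1.1 points back: "Criteria for addition of new systemic treatment for chronic GVHD are defined as per" section 9.0. It also requires a steroid dose of at most 0.2 mg/kg/day at 6 months.
- **Taper.** In 5.3.1 the patient stays on 1 mg/kg every other day until resolution. The next step, 0.7 mg/kg every other day, carries the condition "start after resolution or near resolution of GVHD".
- **Visits.** Section 8.2 sets visits at months 1, 2, 3, 4 and 6 during the first half year. Section 9.1 says: "Response to therapy will be assessed at clinical assessment visits every 3 months from the first day of treatment with GDC-0449". In 8.4, "we use the following transformation between weeks and months when addressing the schedule of assessments" introduces a table in which 1 month is week 4 ± 1 week and 6 months is week 24 ± 1 week.
- **Continuation.** Section 5.5 allows treatment to month 12 "if there is clinical benefit (i.e. PR or CR) after the first 6 cycles". Its list of reasons to stop, which 5.7 uses for removal, names progression but not SD.

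**The concern.** SD usually marks a patient who has neither improved nor worsened. Here it also covers a patient who has improved and then stayed improved for a month, because an earlier response is declared irrelevant. That label triggers mandatory added therapy, removal and an FFS failure.

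For a plateau with substantial residual disease this may be a deliberate rule. For a patient at resolution or near resolution it works against the rest of the plan: the taper needs that patient to hold the state, and 5.5 treats a partial response (PR) or complete response (CR) as benefit. The primary endpoint is at stake. Either a sustained responder is counted as a failure, or the rule is set aside case by case without record, which is the practice variation 9.1.1 sets out to limit.

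**Working it through.** The plan gives no target FFS rate, null rate or power, so there is no figure of its own to reproduce. The check traces the definitions and sets them against the taper and the visits.

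**1. Chain of definitions.** One unchanged month after a response → SD (9.1.2, category 1) → added treatment required, patient off study (9.1.2, closing paragraph) → failure (9.1.1, 10.1.1). The same patient can also satisfy category 3 or 4, since PR and CR are each met by any one organ criterion. No order of precedence is given.

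**2. Taper (5.3.1).** Average daily dose = mean of the two alternating daily doses, or every-other-day dose / 2.

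| Taper weeks | Dose, mg/kg | Average, mg/kg/day |
|---|---|---|
| 1–2 | 1 / 0.5 alternating | 0.75 |
| 3–4 | 1 / 0.25 alternating | 0.625 |
| 5–6 | 1 every other day, held until resolution | 0.50 |
| 7–8 | 0.7 every other day, needs (near) resolution | 0.35 |
| 9–10 | 0.5 every other day | 0.25 |
| 11–12 | 0.4 every other day | 0.20 |

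The steps at 0.35 and 0.25 take 2 + 2 = 4 weeks. If (near) resolution is reached at week R, the limit of 0.2 is met at R + 4 at the earliest. If nothing changes from R, SD is met at R + 4 (R + 3 to R + 5 with the ± 1 week window). The two coincide.

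**3. Who can be affected.** With first improvement at week I, the taper starts at I + 1 at the earliest and 0.2 is reached at I + 11 at the earliest. Meeting the limit by week 24 needs I ≤ 13 and R ≤ 24 − 4 = 20. A held PR short of near resolution stays at 0.50 mg/kg/day and fails on steroid dose anyway, so its 6-month status does not change.

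**4. When the hold is seen.**

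| Schedule | Hold starts at visit | First seen unchanged |
|---|---|---|
| 8.2 | week 8 | week 12 |
| 8.2 | week 12 | week 16 |
| 8.2 | week 16 | week 24 (endpoint visit) |
| 9.1 | week 12 | week 24 (endpoint visit) |

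On the 8.2 visits a hold is seen before month 6 only if it starts by week 12. On the 9.1 schedule that never happens. The calendar in section 7 gives minimum visits, so extra visits are possible but not required.

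**5. Example (assumed scores).** Skin is 2, 1, 0, 0 at weeks 0, 4, 8 and 12, and the eye score is 1 throughout. Assume the investigator judges this near resolution from week 8; 5.3.1 does not define the term. Improvement at week 4 starts the taper at week 5. The 0.7 step starts at 5 + 6 = week 11, 0.2 mg/kg/day is reached at 5 + 10 = week 15, and the 18-week taper is over at 5 + 18 = week 23. No score changes between weeks 8 and 12, so SD is met at week 12 and FFS fails. Without the rule, and with no other failure event, the patient is an FFS success at week 24.

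**6. Size.** 1/12 = 8.3 points per patient; for an assumed 2 or 3 patients, 16.7 or 25.0 points. From an assumed 6/12 failure-free (50.0%, exact 95% CI 21.1–78.9), one reclassified patient gives 5/12 = 41.7% (15.2–72.3), and three give 3/12 = 25.0% (5.5–57.2).

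**The case against.** The strongest reply is the attribution sentence in 9.1.2. A patient with every involved organ at 0 has no disease left for SD to be attributed to, and also meets category 4. A reader might infer that the text definitely fails this patient; it does not. With the attribution sentence and no precedence rule, the text is ambiguous. But that sentence reads as a differential-diagnosis check rather than an exemption for responders, and it does not cover a near-resolved patient with residual disease, as in the example.

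Second, 9.1.1 can be read as setting conditions that must be met before therapy may be added, rather than a trigger, and the FFS bullets count actual addition. Against that, 9.1.2 says added treatment is required, and 9.1.1 makes the need for it a failure. The tension stands.

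Third, a reader might infer that every held PR becomes a wrongful failure, or that the rule contradicts continuation to month 12. Neither is supported. A PR short of near resolution misses the steroid limit anyway. The added-therapy criteria cover only the first six months, so they clash with 5.5 only through patients removed before month 6, and they reach one-year FFS only by carrying those failures forward.

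Fourth, this is a 12-patient single-arm pilot with Kaplan-Meier and descriptive summaries and no decision threshold. No go/no-go decision turns on one patient. The endpoint should still mean what it says.

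**Conclusion.** The point holds for resolved or near-resolved patients. Read literally, 9.1.2 can turn a patient who holds that state for a month, as the taper requires, into an FFS failure. For the near-resolved patient with residual disease the text offers no clear escape; for the fully resolved patient it is ambiguous.

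The affected group is narrow: improvement by week 13, near resolution by week 20, and, on the 8.2 visits, a hold that starts by week 12 if it is to be seen before month 6. If the hold is first seen at the week-24 visit, the plan does not settle whether it counts against 6-month FFS. The number of such patients is unknown. Each moves 6-month FFS by 8.3 points; totals for two or three patients rest on assumed counts. The conclusion assumes that the 5.3.1 taper is followed and that SD is judged against the preceding month, as the sentence on earlier response implies.

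**What to change.** 1. In 9.1.2, add that a patient in CR in all involved organs, or at the resolution or near resolution that permits the 0.7 every-other-day step in 5.3.1, who does not meet PD is not SD and does not require added treatment.
2. State that PD in any organ takes precedence.
3. Keep the plateau rule for patients with residual active GVHD short of near resolution. Barring SD for anyone with a PR in one organ would reverse what reads as a deliberate choice.
4. State in 9.1 that these criteria are applied at the 8.2 visits.
5. For patients already treated, record whether the exempted state was met on the day treatment was added, and list those FFS failures separately.

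The cost is a short addition to 9.1.2, one clarification in 9.1 and one data item per patient given added treatment. The exemption uses a judgement the taper already demands, so no new scale is needed, though near resolution remains a clinical call. The downside is small: a few near-resolved patients stay on study drug longer before other therapy is added.

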4.1 Inclusion Criteria

Yes/No (Response of "no" = patient ineligible)

4.1.1 _____ Age ≥ 18 years.

Because no dosing or adverse event data are currently available on the use of GDC-0449 in patients < 18 years of age, children are excluded from this study.

4.1.2 _____ ECOG performance status ≤ 2 (Karnofsky $\geq 60\%$, see [Appendix A](#)).

4.1.3 _____ Life expectancy of greater than 12 months

4.1.4 _____ Patients must have normal organ and marrow function as defined below:

- | | |
|--|--|
|  Leukocytes | $\geq 3,000/\text{mcL}$ |
|  Absolute neutrophil count | $\geq 1,500/\text{mcL}$ |
|  Platelets | $\geq 50,000/\text{mcL}$ |
|  Total Bilirubin | within normal institutional limits |
|  AST(SGOT)/ALT(SGPT) | $\leq 2.5 \times$ institutional upper limit of normal |
|  Creatinine | $\leq 1.5 \text{ mg/dl}$ |
| OR | |
|  Creatinine Clearance | $\geq 55 \text{ mL/min}$ using the Cockcroft-Gault equation for patients with creatinine |

levels above 1.5 mg/dl.

- 4.1.5** _____ Patients with chronic GVHD diagnosed within 3 years after hematopoietic stem cell transplant (HSCT) for any disease, with any graft, and any conditioning regimen with at least one manifestation secondary to fibrosis, including: sclerodermatous skin changes, dry mouth, dry eye, esophageal strictures, or vaginal GVHD
- 4.1.6** _____ Failure to respond to corticosteroids, defined as:
- Progression of chronic GVHD despite optimal first line therapy (> 0.5 mg/kg/day of prednisone dose equivalent (PDE) for two weeks) or;
 - No improvement after 4-8 weeks of sustained therapy. Sustained therapy should include 2 weeks of > 0.5 mg/kg/day of PDE or;
 - Inability to taper steroid dosage to less than 0.5 mg/kg/day of PDE without worsening of chronic GVHD or;
 - Need for second or third line therapy beyond corticosteroids and calcineurin inhibitors or sirolimus, irrespective of other criteria listed under the current section.

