4.2 Exclusion Criteria

4.2.1 _____ Patients who have had chemotherapy or radiotherapy within 4 weeks (6 weeks for nitrosoureas or mitomycin C) prior to entering the study or those who have not recovered from adverse events due to agents administered more than 4 weeks earlier.

4.2.2 _____ Patients who are receiving any other investigational agents.

4.2.3 _____ Patients with known brain metastases should be excluded from this clinical trial because of their poor prognosis and because they often develop progressive neurologic dysfunction that would confound the evaluation of neurologic and other adverse events.

4.2.4 _____ History of allergic reactions attributed to compounds of similar chemical or biologic composition to GDC-0449

4.2.5 _____ Patients receiving any medications or substances that are strong inducers/inhibitors or substrates of CYP3A4/5, CYP2C9, CYP2C8, or CYP2C19 are ineligible. Because the lists of these agents are constantly changing, it is

important to regularly consult a frequently-updated list such as <http://medicine.iupui.edu/clinpharm/ddis/table.aspx>; medical reference texts such as the Physicians' Desk Reference may also provide this information. As part of the enrollment/informed consent procedures, the patient will be counseled on the risk of interactions with other agents, and what to do if new medications need to be prescribed or if the patient is considering a new over-the-counter medicine or herbal product.

- 4.2.6** _____ Patients with malabsorption syndrome or other condition that would interfere with intestinal absorption. Patients must be able to swallow capsules.
- 4.2.7** _____ Patients with clinically important history of liver disease, including viral or other hepatitis or cirrhosis are ineligible.
- 4.2.8** _____ Patients with uncontrolled hypocalcemia, hypomagnesemia, hyponatremia or hypokalemia defined as less than the lower limit of normal for the institution, despite adequate electrolyte supplementation are excluded from this study.
- 4.2.9** _____ Uncontrolled intercurrent illness including, but not limited to, ongoing or active infection, symptomatic congestive heart failure, unstable angina pectoris, cardiac arrhythmia, or psychiatric illness/social situations that would limit compliance with study requirements.

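### The liver line for partial response does not measure liver response: read literally it needs a normal bilirubin to halve, and read loosely it counts a fall in a test that was never raised

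*Combined protocol and SAP*

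**What the plan says.** Section 9.1.2 lists ten lines for each of PR, CR and progressive disease (PD): nine organ sites and a clinician global score. One line is enough: "Partial Response: This is defined as any one of the following". The liver lines are:

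- PR: "Liver: Decrease by 50% ALT, alkaline phosphatase, and Total bilirubin"
- PD: "Liver: Increase by 2x ULN ALT, alkaline phosphatase, and Total bilirubin"
- CR: "Liver: Normal ALT, alkaline phosphatase, and Total bilirubin after previous elevation of one or more"

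Only the CR line asks for an earlier abnormal value. The PR line does not name the visit against which the fall is measured.

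Section 4.1.4 requires total bilirubin at entry to be "within normal institutional limits". It allows ALT up to 2.5 times the upper limit of normal (ULN) and sets no limit for alkaline phosphatase. Section 4.2.7 adds: "Patients with clinically important history of liver disease, including viral or other hepatitis or cirrhosis are ineligible".

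Clinical response at 6 months under 9.1.2 is a secondary endpoint (10.1.2), to be tabulated by organ and overall (10.2). PR or CR after six cycles also governs extension of treatment (5.5). The closing paragraph of 9.1.2 ties stable disease and PD to added systemic therapy and departure from the study, and asks that those conditions be due to chronic GVHD with other causes ruled out. That paragraph does not cover PR.

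**The concern.** The PR line joins three tests with *and*, although one of them is required to be normal when the patient enters. A patient with real biochemical improvement can therefore fail the line because bilirubin had no abnormality to correct.

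The natural way to rescue the line is to read the tests as alternatives, but this opens the opposite error. Most other PR lines need a fall in an involvement score, which cannot drop below zero. A normal laboratory value can halve. Without a prior-elevation condition, that fall alone would make an overall PR.

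At stake are the 6-month response rate and the liver row of the organ table. Two assessors could score the same patient differently, and both could point to the text.

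**Working it through.** The plan gives no calculated figure on this point, and the 12 patients are stated without a derivation, so there is nothing to reproduce. The check applies the liver lines to example patients who meet the entry limits.

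**Rules applied** (values in multiples of ULN)

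- PR, *and* reading: all three tests at or below 0.5 × the starting value.
- PR, *any* reading: at least one test at or below 0.5 × the starting value.
- CR: at least one test above 1 at the start, and all three at or below 1 afterwards.
- PD, *and* reading: all three tests rise by at least 2. PD, *any* reading: at least one does.

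| Patient | ALT | Alk. phos. | Bilirubin | PR, *and* | PR, *any* | CR |
|---|---|---|---|---|---|---|
| A | 2.5 → 1.2 | 3.0 → 1.4 | 0.6 → 0.6 | no | yes | no |
| B | 1.5 → 0.9 | 0.8 → 0.8 | 0.6 → 0.6 | no | no | yes |
| C | 0.8 → 0.4 | 0.8 → 0.8 | 0.6 → 0.6 | no | yes | no |
| D | 2.5 → 1.2 | 3.0 → 1.4 | 1.0 → 0.5 | yes | yes | no |

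- **A.** ALT falls by 1 − 1.2/2.5 = 52% and alkaline phosphatase by 1 − 1.4/3.0 = 53%. Under the *and* reading this is no liver response, solely because a normal bilirubin did not move.
- **D.** The enzyme values are those of A. The call changes only because bilirubin went from the upper limit of normal to half of it, a change within the normal range.
- **B.** This is a CR but not a PR. ALT falls by 1 − 0.9/1.5 = 40%, so B would miss any 50% test, and that alone is harmless because CR ranks above PR. Starting B's ALT at 2.5 instead makes the fall 1 − 0.9/2.5 = 64%. Literal PR is still not met, while CR is. That is the inversion.
- **C.** No test is ever raised. Under the *any* reading C is a liver PR, and so an overall PR.

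For PD, a patient E with ALT 1.0 → 3.5 (a rise of 2.5) and the other tests unchanged and normal is not a PD under *and*, but is a PD under *any*.

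**Size of one error.** 1/12 = 8.3 percentage points of the response rate.

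**Frequency of C by chance, as an illustration only.** Take a stable analyte with within-patient coefficient of variation CV and lognormal variation. The chance that one later value is half the first or less is p = Φ(ln 0.5 / (√2 σ)), with σ² = ln(1 + CV²). For CV 0.20, σ² = ln 1.04 = 0.0392, σ = 0.198, and p = Φ(−0.693/0.280) = Φ(−2.475) = 0.7%. The chance of at least one such patient in 12 is 1 − (1 − p)¹². For three analytes, p is replaced by 1 − (1 − p)³.

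| Assumed CV | p, ALT alone | ≥1 of 12, ALT alone | ≥1 of 12, any of three |
|---|---|---|---|
| 0.10 | about 0% | about 0% | about 0% |
| 0.20 | 0.7% | 8% | 21% |
| 0.30 | 4.8% | 44% | 83% |
| 0.40 | 10.2% | 72% | 98% |

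The CVs are assumptions, the same for all three tests. The three tests are treated as independent, and one comparison per patient is counted. The documents supply none of this.

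**The case against.** Several objections have force.

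- **Literal PR is not impossible.** A reader might infer that liver PR can never be met. Patient D shows otherwise. The entry limit also binds only at screening, and if the comparison were with an on-study peak, bilirubin could have been raised. This stands: the line is badly aimed, not unreachable.
- **A third reading works.** If each test that was raised must halve, the line is sensible and agrees with the CR line. This also stands, but the protocol does not say so.
- **Overall PR has nine other routes**, including the global score. The liver is not among the fibrotic manifestations named in 4.1.5, and clinically important liver disease is excluded. The *and* fault therefore changes an overall call only when enzymes improve short of CR and nothing else responds. This limits the harm from the *and* reading, but not the false PRs under *any*.
- **False PRs need not be common.** The table above might suggest that they are. It runs from almost never to nearly always according to an assumed CV, so it establishes no rate. A liver-only PR would also show in the organ table, and no test is planned on response.
- **PD is a different case.** A reader might extend the bilirubin argument to PD. It does not carry over, because a normal bilirubin can rise, and PD has the attribution sentence that PR lacks. What remains for PD is the ambiguity of *and*.
- **The primary endpoint.** A reader might infer that failure-free survival is compromised. Its definition in 9.1.1 and 10.1.1 does not use PR. A miscalled liver could reach it only through a decision to add therapy, and the documents do not show that this would occur.

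**Conclusion.** The point holds for the liver PR line. As written it either withholds PR from a patient whose raised enzymes have more than halved, or, if loosened to *any*, grants PR for a fall in a normal test. The first result follows directly from the text and the entry limit for bilirubin. The second depends on reading *and* as *any*, and on no other text confining PR to an involved liver; none was found.

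The CR line is sound, so it would be too strong to say that the liver criteria as a whole cannot work. The size is 8.3 points per miscalled patient, with no frequency available from the documents. It is worth correcting because a stated rule gives wrong calls on a named secondary endpoint and the remedy is already in the adjoining CR line. Neither the sample size nor any test is affected.

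**What to change.** For the 6-month clinical response endpoint (10.1.2 and 10.2), amend the liver PR line so that it:

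1. is scored only after previous elevation of one or more of ALT, alkaline phosphatase and bilirubin, as the CR line already requires;
2. applies the 50% fall to the test or tests that were elevated;
3. names the visit with which the comparison is made.

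Taking the starting values as the comparator, patient A becomes a liver PR, B stays a CR, C is not scored for liver PR, and D is a PR on its two raised enzymes without needing the bilirubin to move.

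The cost is one line of wording and a little re-scoring. The chemistry panel in 8.1 contains all three tests, and the study calendar already schedules it at the assessment visits.

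The PD line has the same *and* wording. Because PD leads to added systemic therapy and removal from study (9.1.2), and PR governs extension of treatment (5.5), the sponsor should reconcile those passages and state which definition each relies on. No PD threshold or treatment rule is proposed here. Liver PD should not be restricted to patients with raised tests at baseline, since that would hide new liver GVHD in patients who entered with normal values.
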